#### **3.2 Secondary Endpoint(s)/Event(s)/Outcome(s):**

Secondary outcomes include brain resting state functional connectivity and various psychosocial factors related to participants' experiences with SCI, such as change in mood, satisfaction with life, and community integration.

### **4.0 Study Intervention(s)/Investigational Agent(s)**

#### **4.1 Description:**

Intervention: brivaracetam or placebo administration. Because this is an off-label use of an FDA approved drug, we received an Investigational New Drug (IND) designation from the FDA for this study (IND Holder [name], #150388). RxArtisans Pharmacy (Wayzata, MN) will FedEx the drug to the participant directly or to the Rehabilitation Department Boynton Bridge, University of Minnesota (UMN) for distribution, and study staff will send an email notification that the drug has been sent by overnight mail. To minimize wasting of drug, RxArtisans will dispense and ship prescriptions for participants concurrent with the ramp-up schedule (weekly, biweekly, or as requested by study doctor). Once maximum dose is stabilized, RxArtisans will dispense and ship prescriptions monthly. Participants will be

## MEDICAL PROTOCOL (HRP-590)

PROTOCOL TITLE: Brivaracetam to Reduce Neuropathic Pain in Chronic SCI: A Pilot Clinical Trial  
VERSION DATE: 03/18/2024

asked to verify by phone or email receipt of study drug and initiation of the treatment course.

Drug dosage will be individually titrated for each participant with a goal of 100mg BID according to the following dose escalation protocol that we use clinically: 50mg BID X 2 weeks followed by 50mg TID X 2 weeks followed by 100mg BID X for 48 days, as tolerated. Participants will be allowed to reduce the dose of brivaracetam if they experience unacceptable side effects defined as increased somnolence according to routine clinical practice with other drugs in this class used for pain.

In the case of intolerance at 50mg BID during dose escalation, the dose will be reduced to 25mg daily or 25mg BID. In the case of intolerance, the dose will be reduced down 1 step to last tolerated dose. For intolerance at 100mg BID, the dose will be reduced to 50mg TID. For intolerance at 50mg TID, the dose will be reduced to 50mg BID. A dose of 50mg BID or higher must be maintained to complete the trial.

Drug discontinuation at study completion will be done according to the following protocol we use clinically that will be initiated for 2 weeks after end of study testing: Reduction to 50mg BID X 1 week followed by 50mg daily X 1 week. For those at the highest study tolerated dose of 50mg BID, the dose will be reduced to 50mg daily X 1 week and then stopped. At the end of study participants will be asked to mail empty bottles for pill counts with self-addressed and prepaid packaging, and will review the medication diaries via phone. We will use the clinically meaningful reduction in Brief Pain Inventory score of 1 point or more as the definition of “drug response” in this study. University of Minnesota Investigational Drug Services (IDS) will register the study, while Rx Artisans will be dispensing the drug.

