## 5.0 Procedures Involved

### 5.1 Study Design:

This is a multi-center randomized, double-blinded placebo-controlled pilot clinical trial. Each site (Swedish Medical Center/Craig Hospital, UMN) will enroll and study 20 adults, 18 years of age and older with SCI. [name] will serve as PI, and [name] will serve as Co-I at UMN (local site). MRI data analysis will be conducted by [name] (Harvard University). [name] will receive a deidentified dataset and will have no human subject interactions. Research activities at the Swedish Medical Center/Craig Hospital will be conducted under a separate IRB protocol at Craig Hospital.

Participants who meet the eligibility criteria will be randomly assigned to active drug (escalating brivaracetam dose to 100 mg twice daily for 3 months) or placebo based on a randomization schedule developed by our biostatistician. This is a simple computer generated 1:1 scheme that randomly assigns participants to arm A or arm B. Study participants, research coordinators, and study personnel involved in outcomes assessments and analyses will all be blinded. The drug will be provided by RxArtisans pharmacy in Wayzata, MN. The active and placebo capsules will have identical appearance and consistency. Treatment assignment will be known only to the investigational drug pharmacies (RxArtisans). We have registered this pilot study with National Institutes of Health (NIH) clinical trials registry, [www.clinicaltrials.gov](http://www.clinicaltrials.gov) (NCT04379011). The pilot data generated by this effort will be used to power a subsequent multi-center clinical trial.

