CDE-recommended questionnaires relating to pain, mood, active suicidality, satisfaction with life, kinesiophobia, sleep quality, and community integration will be administered. Participants will then begin 3 months of active treatment (100 mg BID) or placebo. All participants will receive a medication diary to track study drug compliance and to record medication use. Blinded data collectors will perform weekly check-in calls to assess for medication-related adverse events including the PHQ-9 for changes in mood and suicidality. Reported AEs identified in these calls will be documented and immediately shared with the PI for review.

End of study assessments will be repeated 3 months after baseline testing and again 1 month after cessation of study medication (active/placebo).

Lab work will be repeated to confirm normal renal function, absence of liver cirrhosis, and absence of pregnancy in individuals of childbearing potential at the end of the study. Specimen collection and analysis will either occur at the Fairview Clinical Research Unit or with the participant's

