**Table 1. Study Procedures**

Study Task	Pre-Screen	Visit 1*	Visit 2*	Visits 3 (end of study testing)	2 weeks drug dose reduction (after end of study testing)	Visit 4 (long-term follow-up)
Pre-Screening Phone Survey	X					
Consent/randomization		X				
MRI Brain Scan (optional)			X	X		
Blood draw for biomarkers (optional)			X	X		
Physical health exam, health history screening, surveys		X		X		X
Initiate intervention			X			
Dispense 3-month drug supply			X			
Reminder check-in: begin 2-week drug dose reduction protocol after end of study testing					X	
Limited safety labs (blood draw, required)				X		
Pill count/medication diary review					X	
Pregnancy test (for women of child-bearing potential)				X		
Adverse Events	Assessed weekly (phone)					

\*Visits 1 and 2 may be combined for participant convenience

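### Section 4.1 lists 76 days of dosing, but the course and the end-of-study visit are set at 3 months, so no dose is specified for the last days before Visit 3

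*Combined protocol and SAP*

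**What the plan says.** **Regimen.** Section 4.1 gives the dosing steps as "50mg BID X 2 weeks followed by 50mg TID X 2 weeks followed by 100mg BID X for 48 days, as tolerated". No other section gives a day-by-day schedule. Section 4.1 also requires participants to stay on at least 50 mg twice daily in order to complete the trial.

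**Length of course.** Section 5.1 describes the active arm as "escalating brivaracetam dose to 100 mg twice daily for 3 months". Section 5.2 says: "Participants will then begin 3 months of active treatment (100 mg BID) or placebo". Section 5.5 puts the second scan after a 3-month course.

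**Time of testing.** Section 5.2 says: "End of study assessments will be repeated 3 months after baseline testing". This is Visit 3 in Table 1.

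**Taper.** Section 4.1 describes a discontinuation protocol "that will be initiated for 2 weeks after end of study testing", which for most participants is "Reduction to 50mg BID X 1 week followed by 50mg daily X 1 week". Those whose highest dose is 50 mg BID take 50 mg daily for one week and then stop. Table 1 also places the taper after Visit 3.

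**The concern.** Visit 3 supplies the follow-up value of the primary pain outcome and the second MRI. Section 15.1 analyses pain change from baseline to the end of a 3-month treatment, and Section 15.2 says the pilot's effect sizes and standard errors will be used to plan the follow-up trial. A reader of those estimates needs to know how long participants had been treated when they were assessed, and whether they were still on the maintenance dose.

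The protocol does not settle this. Its schedule ends at day 76, its visit falls later, and no sentence says what is taken in between. Sites or participants could resolve the conflict in different ways, which would add avoidable variation in exposure at the visit that matters most.

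**Working it through.** **Inputs from the documents**
- Ramp-up and maintenance (Section 4.1): 2 weeks, 2 weeks, 48 days.
- Treatment length and time of Visit 3 (Sections 5.1, 5.2, 5.5): 3 months.
- Taper (Section 4.1, Table 1): 2 weeks, after testing.

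**Assumptions**
- The documents do not convert 3 months into days. I take 90 to 91 days as the main case and vary it.
- I take the first dose on the baseline date. Table 1 starts the intervention at Visit 2 and states no lag.

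**Step 1. Length of the listed schedule.** 14 + 14 + 48 = 76 days, which is 76 / 7 = 10.9 weeks, or about 2.5 months.

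**Step 2. Comparison with 3 months.** Gap = days to Visit 3 − 76.

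| Meaning of 3 months | Days | Gap |
|---|---|---|
| 12 weeks | 84 | 8 |
| 3 × 30 days | 90 | 14 |
| 13 weeks | 91 | 15 |
| Calendar months, shortest to longest | 89 to 92 | 13 to 16 |

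No meaning of 3 months gives 76 days. In the main case the gap is 14/90 = 15.6% to 15/91 = 16.5% of the course.

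**Step 3. A later first dose.** If dosing starts 7 days after baseline and Visit 3 is counted from baseline, the gap is 90 − 76 − 7 = 7 or 91 − 76 − 7 = 8 days. Only a lag of 14 to 15 days closes it.

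**Step 4. Maintenance needed to reach Visit 3.** The ramp-up takes 28 days. Maintenance would have to run 90 − 28 = 62 or 91 − 28 = 63 days, against the 48 listed.

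**Step 5. Where 48 may come from.** 76 + 14 taper days = 90. The listed figure fits 3 months if the taper is counted inside them, but the current text puts the taper after testing at 3 months. The Revision History records that version 3.0 moved testing ahead of the ramp-down, so the 48 days may be a remnant of the older order. That is an inference; the inconsistency lies in the current text.

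**Step 6. What the rest of Section 4.1 implies.** A minimum dose must be kept up to complete the trial, and the step after testing is a reduction, which presupposes someone still taking drug. Both point to participants being on drug at Visit 3. It follows that the 48 days and a 3-month Visit 3 cannot both stand. Either maintenance is too short on paper or the visit was meant for about day 76.

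**The case against.** **Neither plausible intention puts Visit 3 off drug.** Either Visit 3 falls near day 76 and the taper ends at day 90, or maintenance continues to a 3-month Visit 3. In both cases pain and MRI are measured on drug and a taper follows. This stands, and it limits the point to an inconsistency in duration and visit timing.

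A reader might infer more than the documents support:
- *That dosing stops before Visit 3 and the taper restarts drug in people already off it.* No sentence orders a stop at day 76. That outcome follows only if the 48 days are applied literally, against the minimum-dose rule and the post-test reduction in the same section.
- *That participants face an untapered withdrawal.* Section 13.1 does name a lowered seizure threshold as the risk of rapid withdrawal, but the risk arises here only under that same literal reading. Section 8.2 excludes epilepsy and active seizure treatment, Section 5.2 provides weekly calls, and Sections 5.2, 12.2 and 21.1 put discontinuation under medical supervision.
- *That the supply runs out.* Table 1 has the row "Dispense 3-month drug supply", but Section 4.1 describes shipments that follow the ramp-up and then go out monthly, which can cover both a longer course and the taper.

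**Flexible wording.** Titration to tolerance governs the dose level and does not lengthen the 48 days. Section 5.3 gives participation as roughly three months, which loosens the calendar but supplies no dose for the missing days.

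**Limited consequence.** Daily pain diaries record pain throughout treatment, and the version 8.0 entry in the Revision History says enrollment is complete. Both are fair, and they are reasons to rate the point as minor. They do not reconcile the text.

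**Conclusion.** Wrong as written: an internal inconsistency, minor in weight. The arithmetic of 76 listed days against a stated 3 months is certain. The size of the unspecified interval depends on two things the documents leave open, namely the length of 3 months in days and the lag from baseline to first dose. It is 14 to 15 days in the main case and 8 days at 12 weeks, both with dosing from baseline, and smaller with a later start.

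The documents do not show that anyone was, or was meant to be, assessed off drug. What remains unknown from the protocol is the treatment duration that the Visit 3 estimates represent.

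**What to change.** **Text.** In Section 4.1, replace the 48 days with *100 mg BID or highest tolerated dose until Visit 3*, which is about 62 to 63 days after the ramp-up. This keeps the stated 3-month course and on-drug assessment, and the taper then follows testing without a gap. If Visit 3 was meant for about day 76, keep the 48 days and instead restate the visit time and treatment length in Sections 5.1, 5.2 and 5.5.

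**Reporting.** As enrollment is complete, report by arm the actual treatment duration and the days from last maintenance dose to Visit 3. The source already exists: "All participants will receive a medication diary to track study drug compliance and to record medication use".

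**Cost.** The first option changes one phrase. It lengthens the written regimen by 14 to 15 days, within the course already described, but in an IND study this is a protocol amendment and not only an edit. The second option changes several statements and adds no exposure. The prospective gain from either is now small. The report needs no new data collection and tells the designers of the follow-up trial what exposure the pilot estimates reflect.

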*Moorong Self-Efficacy Scale (MSES)*. This is a 16-item scale that assesses self-efficacy in performing functional activities of daily living individuals with SCI.

*Pain Catastrophizing Scale (PCS)*. This 13-item self-report measure is designed to assess catastrophic thinking related to pain among adults with or without chronic pain.

*Perceived Disability Index (PDI)*. This is a brief, self-report instrument developed to assess self-perception of disability.

*Penn Spasm Frequency Scale (PSFS)*. This is a self-report measure that assess a patient's perception of spasticity frequency and severity following a spinal cord injury.

*Intervention Expectations*. This self-report will assess what participants expect their outcomes to be during and after their participation in the study.

*Concurrent Pain Medication Use*. Although pain medications can confound the analgesic effects of brivaracetam, we consider it to be unethical to require participants to discontinue pharmacologic treatment for pain over the course of the study as a criterion for enrollment. In addition, to increase generalizability, it is important to recruit participants using pain medications. Therefore, we will record pain medication use over the course of the trial and consider this in the analysis.

*Pain Intensity and Medication Use Diary*. We will monitor daily pain reports and patient medication throughout the course of the study using a Pain Intensity and Medication Use Diary. Participants will be asked to record daily pain ratings (highest pain 0-10, lowest pain 0-10, and average pain 0-10) and any pain medication use. This diary will be started 1 week prior to drug treatment and maintained until completion of the study.

*Assessment of Cortical Activity by Brain MRI*. MRI scans of the brain will be performed for participants who are eligible and provide consent to MRI. Testing will be performed at baseline and end of study. We will use 3 Tesla Magnetic Resonance Imaging to collect i) brain structure (Multi Echo Magnetization Prepared Rapid Acquisition Gradient Echo, MEMPRAGE) ii) brain white matter integrity (Diffusion Weighted Imaging, DWI), iii) brain resting state functional connectivity (resting state functional Magnetic Resonance Imaging, rsfMRI), and iv) evoked responses to Motor Imagery

**MEDICAL PROTOCOL (HRP-590)****PROTOCOL TITLE: Brivaracetam to Reduce Neuropathic Pain in Chronic SCI: A Pilot Clinical Trial**  

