## MEDICAL PROTOCOL (HRP-590)

PROTOCOL TITLE: Brivaracetam to Reduce Neuropathic Pain in Chronic SCI: A Pilot Clinical Trial  
VERSION DATE: 03/18/2024

---

\*\*Medical clearance must be clinically obtained from participants' primary care provider or other healthcare provider within 1 month prior to visit 1

*Study drop criteria.* Participants will be removed from the study for safety reasons including drug intolerance, drug allergy, drug contraindications, development of depression, aggressive behavior, anxiety, or suicidality, or evidence of brivaracetam adverse events according to the manufacturer's prescribing guide (package insert). Poor drug compliance will be recorded for consideration during the analysis but will not be cause for removal from this study. In the case of drug intolerance, participants will reduce the drug dose under medical supervision of the PI until the drug can be safely discontinued.

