### *12.3 Termination Procedures:*

Participation may be terminated due to drug intolerance or allergy and based on clinical judgement of the study team. All data collected will be retained and analyzed unless the participant specifically requests to have their data withdrawn from the analysis.

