### 18.2 Data Safety Monitoring

Plan for Monitoring Safety. The safety environment of UMN participants will be overseen and monitored by [name]. We will monitor to assure that participants meet eligibility criteria; that the informed consent process is conducted appropriately, that the data will be collected and analyzed as specified in the protocol, that adverse events (defined below) are reviewed promptly and reported as required (detailed below), that dropouts are documented, and that primary and secondary endpoints are evaluated. According to the data safety-monitoring plan, study participation will be terminated immediately in the event of injury or increased morbidity (drug intolerance). Data and all procedures will be monitored at each measurement time point and monthly throughout the duration of the study to ensure the safety of participants.

Unblinded Study Physician/Medical Monitor. Our safety monitoring plan also includes an independent medical monitor: [name] (Thomas Jefferson University). [name] will review all reported adverse events on a monthly basis and as needed with the PI, [name], who will inform [name] immediately of all study-related unanticipated problems involving risk to volunteers or others, serious adverse events, and all volunteer deaths associated with the protocol, and provide an unbiased written report of the event to the IRB and FDA. The medical monitor will comment on the outcomes of the event or problem, and in the case of a serious adverse event or death, comment on the relationship to

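### Removing participants from the study, not only from the drug, for intolerance loses their Visit 3 BPI, and Section 15 has no rule for the missing outcome

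*Combined protocol and SAP*

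**What the plan says.** Section 4.1 titrates towards 100 mg BID and allows step-downs for intolerance, including one below the floor: "In the case of intolerance at 50mg BID during dose escalation, the dose will be reduced to 25mg daily or 25mg BID". It then states: "A dose of 50mg BID or higher must be maintained to complete the trial". It does not say whether 25 mg is a temporary step or a route out of the trial.

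Three other places deal with leaving for intolerance:

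- Section 5.2, study drop criteria: "Participants will be removed from the study for safety reasons including drug intolerance, drug allergy, drug contraindications". The same paragraph says the dose is brought down under the PI's supervision until the drug can be stopped.
- Section 18.2: "study participation will be terminated immediately in the event of injury or increased morbidity (drug intolerance".
- Section 12.3, more loosely: "Participation may be terminated due to drug intolerance or allergy and based on clinical judgement of the study team". It adds: "All data collected will be retained and analyzed unless the participant specifically requests to have their data withdrawn from the analysis".

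Section 12.2 covers only a safe taper on withdrawal. Table 1 places the surveys, which include the BPI, at Visits 1, 3 and 4. Section 15.1 analyses outcomes at baseline and 3 months by linear regression with group, time and their interaction.

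**The concern.** Stopping a drug that a person cannot tolerate is right. Stopping the assessments as well is a separate decision, and here it costs the primary efficacy outcome. A participant removed at week 5, for example, has a baseline BPI and nothing later that the Aim 1 analysis can use.

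Intolerance is tied to treatment. Section 4.1 names somnolence as the trigger for dose reduction, and 5.2 lists depression, aggression, anxiety and suicidality among the grounds for removal. Section 13.1 lists all of these as foreseeable risks. Loss could therefore be heavier on active drug, and the groups compared at Visit 3 might no longer be the groups that were randomised.

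The pilot exists to supply effect sizes and standard errors for a larger trial (15.2). An estimate from those who tolerated the drug answers a different question from the one that trial would face. The Aim 2 comparison of responders with non-responders is touched as well: response is defined by BPI reduction (3.1), so an active-arm participant without Visit 3 cannot be classified.

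**Working it through.** The plan gives no power, SD, dropout or intolerance figure, so there is no stated number to reproduce. The check has two parts.

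**1. Does removal lose the outcome?**

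- Surveys are at Visits 1, 3 and 4 (Table 1). The taper starts after end-of-study testing (4.1), so Visit 3 is on treatment and Visit 4 is off it.
- The weekly calls collect adverse events and the PHQ-9 (5.2), not the BPI.
- The Aim 1 analysis uses baseline and 3 months (15.1), so Visit 4 is outside it.
- Section 12.2 describes no BPI at early exit, and Section 15 describes no handling of a missing 3-month value. It does not say whether a participant with only a baseline BPI stays in the regression. If so, that person adds to the baseline mean only.

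So a participant removed before 3 months contributes no post-baseline BPI to the primary comparison.

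**2. How much could it matter?** Every clinical input here is an assumption.

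- Arm size: 10 per arm if 20 are enrolled in total (23.1), or 20 per arm if 20 are enrolled at each of two sites (5.1), both at 1:1.
- Share lost before Visit 3: qA on active drug, qP on placebo, with qA − qP from 0.1 to 0.3.
- d = mean BPI reduction in those retained minus the mean reduction those lost would have had. It is taken as 1 to 2 points, of either sign, and equal in both arms.
- SD of BPI change: 2.

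If an arm's retained mean is r, its all-randomised mean is r − q × d. The retained-only difference therefore departs from the all-randomised difference by

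shift = (qA − qP) × d

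- Smallest: 0.1 × 1 = 0.1
- Largest: 0.3 × 2 = 0.6
- With d negative: −0.1 to −0.6
- With qA = qP: 0

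The standard error should use the numbers retained. With loss on active drug only, SE = 2 × √(1/nA + 1/nP):

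| Per arm | Extra loss on active | Retained, active v placebo | SE | Shift | Shift / SE |
|---|---|---|---|---|---|
| 10 | 10% | 9 v 10 | 0.919 | 0.1 | 0.11 |
| 10 | 30% | 7 v 10 | 0.986 | 0.6 | 0.61 |
| 20 | 10% | 18 v 20 | 0.650 | 0.1 | 0.15 |
| 20 | 30% | 14 v 20 | 0.697 | 0.6 | 0.86 |

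These ratios depend on the SD. At 14 v 20, SE = SD × √(1/14 + 1/20) = SD × 0.348, so a 0.6-point shift exceeds one SE once the SD is below 0.6/0.348, about 1.7.

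**The case against.** The strongest reply is that the rules are conditional and largely coherent. Sections 4.1 and 5.2 can be read in sequence: step down, and if 50 mg BID cannot be held, taper and leave. Section 12.3 leaves termination to judgement, and 4.1 never literally says that a participant below the floor misses Visit 3. This much stands. A reader might infer that everyone who steps down to 25 mg leaves, or that the removal rule in 5.2 cancels the step-downs in 4.1. The documents support neither. But 5.2 and 18.2 do state removal from the study, and failing to complete the trial reads naturally the same way.

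A second reply is that other data fill the gap. Section 12.3 promises to keep and analyse what was collected, but that cannot supply a BPI that was never taken. Visit 4 is timed from drug cessation, but it is off treatment and outside the Aim 1 analysis, and removal from the study may preclude it. For the pain diary, 5.2 says: "This diary will be started 1 week prior to drug treatment and maintained until completion of the study". A reader might infer that early leavers' ratings are in hand. The only diary review described is at the end of the study (4.1, Table 1), and no step retrieves a diary from someone who leaves early. Section 15 does not name the diary.

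A third reply is that this is a pilot aimed at estimation, that the illustrated shift is below one SE, and that enrollment is complete. This limits the reach of the fix and the urgency of the point. It does not remove the point, because the estimate is what the pilot is for.

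**Conclusion.** The point holds in conditional form. Where participants are removed for intolerance before 3 months, the plan loses their primary efficacy outcome for a reason that may be related to treatment, and Section 15 has no rule for that loss. This follows from the text and needs no assumption.

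The size does need assumptions. The illustration gives a shift of 0.1 to 0.6 BPI points in either direction, or 0.11 to 0.61 SE at 10 per arm and 0.15 to 0.86 SE at 20 per arm. It rests on an assumed SD of 2, 10 to 30 points more loss on active drug and a 1 to 2 point difference between those lost and those retained. A smaller SD gives larger ratios.

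A reader might infer that the rule favours brivaracetam. The documents do not show that. The estimate is overstated if those lost would have had less relief, understated if they would have had more, and unaffected under the formula if the arms lose equal shares. With no intolerance rate given, size and direction are unknown.

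**What to change.** - In 4.1, the drop criteria in 5.2, 12.3 and 18.2, state that intolerance or a dose below 50 mg BID reduces or stops the drug, with a physician-supervised taper, and does not end follow-up unless consent is withdrawn. Changing the floor in 4.1 alone would leave the removal rules in force.
- Obtain the Visit 3 BPI and safety assessments 3 months after baseline for every randomised participant, virtually if needed (5.2 already allows virtual participation), and analyse each in the randomised arm.
- For participants already past Visit 3, report by arm how many fell below 50 mg BID and how many left before Visit 3, with reasons. Section 18.2 already requires dropouts to be documented.
- Where early leavers' diaries were in fact retrieved, add a by-arm summary of weekly mean average pain up to exit. It is supportive only: it stops at exit and is not the BPI.

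The dose and taper for anyone on 25 mg remain with the study physician.

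The cost is a few sentences by amendment, using a visit already scheduled. Including people at low or no dose dilutes the estimated effect, slightly if few are affected. If those off the drug had no benefit and placebo change were nil, a 1.0-point effect among those who stay would become 1.0 × 0.9 = 0.9 with 10% off the drug and 1.0 × 0.7 = 0.7 with 30%. The Revision History entry for version 8.0 records enrollment as complete, so the follow-up change can help only participants not yet past Visit 3, possibly few.
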